3.2.2 Safety assessments

3.2.2.1 Adverse events and common treatment responses

All AEs reported by study subjects, investigators, or other study staff after the time of informed consent through the last study visit will be recorded. Events will be recorded regardless of causality.

A subject diary will be dispensed on the day of treatment (Day 1). Diaries will be reviewed by study staff at the Week 2 visit and re-dispensed for final collection at the Week 6 visit. Completed diaries will also be reviewed by study staff at the Week 6 visit. For subjects receiving an optional touch-up treatment at Week 2, the initial diary will be collected with only two (2) weeks of diary entries completed and a second diary will be dispensed and collected at Week 6. Subjects will be asked to record daily on the diary any pre-defined Common Treatment Site Responses (CTRs) that may occur. These CTRs will include: swelling; firmness; lumps/bumps; bruising; pain; tenderness upon pressing; redness; discoloration (not redness or bruising); itching; stinging/burning; and numbness. The treating investigator will review and initial the subject diary and determine if any entries should be reported as AEs. The investigator may also determine that a CTR will not be reported as a physician-reported AE.

Additional information on safety assessments and procedures is presented in [Section 7](#).

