- Administer Subject Pain-Preference Assessment (three questions) after treatment of both NLFs (i.e., immediately after the time-zero pain VAS assessment).

Additional visit 1 assessments:

- Record any AEs.
- Dispense subject diary and discuss completion instructions.
- Schedule 72-hour follow-up phone call.
- Schedule Visit 2.

Follow-up phone call (72-hours post treatment): Day 4 (\pm 1 day)

- Review and record changes in concomitant medications/procedures.
- Review and record any AEs reported by the subject.
- If subject reports a safety concern, arrange an unscheduled visit to address.
- Remind subject to record CTRs in the subject diary.
- Schedule and/or confirm Visit 2.

Visit 2 (Week 2): Day 14 (+ 3 days)

- Review and record any changes in concomitant medications/procedures.
- Review and record any adverse events.
- Review and collect subject diary. Record subject-reported CTRs in the eCRF. The investigator will review and initial the diary and determine if any entries should also be recorded as AEs on the AE eCRF.

For subjects receiving a touch-up injection at Week 2:

All subjects without ongoing, treatment-related, investigator-reported AEs are eligible for an optional touch-up treatment, at the investigator's discretion and to achieve optimal correction, at Week 2.

- Perform urine pregnancy test (if female of childbearing potential).
- Administer touch-up injection, **not to exceed the maximum allowable injection volume of 3 mL per NLF over the two treatment sessions (initial injection on Day 1 and optional touch-up injection at Week 2)**.
- Dispense subject diary and discuss completion instructions.

Visit 3 (Week 6): Day 42 (+ 3 days)

- Review and record any changes in concomitant medications/procedures.
- Review and record any adverse events.
- Perform urine pregnancy test (if female of childbearing potential).
- Take standardized NLF photographs.
- Have blinded evaluator independently perform the Merz Nasolabial Fold (NLF) Scale assessment.
 - **NOTE:** Every effort should be made to ensure that the same blinded evaluator perform the NLF scale assessment at both visits.
- [REDACTED]
- [REDACTED]
- [REDACTED]
- [REDACTED]
- [REDACTED]
- [REDACTED]
- Review and collect subject diary. Record subject-reported CTRs in the eCRF. The investigator will review and initial the diary and determine if any entries should also be recorded as AEs on the AE eCRF.

5.1.1 *Scheduled visits*

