7.4 Special Statistical/Analytical Issues

7.4.1 Discontinuations and Missing Data

Imputation of effectiveness data

Observed Cases (OC)

- For the OC method, there will be no missing value imputations conducted. All effectiveness data will be analyzed as observed data.

Last Observation Carried Forward (LOCF)

- For the LOCF, in the analysis of the secondary effectiveness variable the subjects who have a missing score on the Merz NLF scale at Week 6 will have their latest available assessment (from the early discontinuation or unscheduled visit if available; failing

that, from the baseline visit) carried forward and imputed into the missing Week 6 assessment.

Imputation of safety data

For partial or completely missing start date of adverse events, the following imputation rules related to any treatment period will be used if applicable:

- If only the day is missing for any date used in a calculation, the 1st will be used to replace the missing day. If the new estimated date falls before the date of first dose, while the known month and year match the month and year of the first dose, the date of first dose will be used as the new estimated date.
- If the day and the month are missing, no estimation will be performed. However, if the year of onset is the same or greater than the year of the first dose date, the AEs will be considered treatment emergent and included in the summary tables.
- AEs with completely missing onset dates will be considered treatment emergent; no estimation of the dates will be performed.

Duration of CTRs would be computed using the following logic:

- Each subject is expected to have diary entries from Day 1 (day of the initial injection) up to and including Day 42 or the day of their completion/discontinuation, whichever comes first. If any subject does not have a diary entry for any of the required days, then for the purposes of CTR analysis it will be assumed that on the missing days they had all those CTRs (if any) that they had on the day before or on the day after the missing day, with the same severity.
- For any CTR with an uninterrupted single episode event, the duration will be computed as the days from the beginning of event to last date of event.
- For any CTR with multiple episodes, the CTR will be regarded as a continuous event if the date between paired episodes is not more than 1 day apart.

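### Protocol 5.1 and 3.2.2.1 disagree on whether subjects without a touch-up keep a diary after Week 2, and the SAP fill rule has no gap limit to contain the result

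*Protocol*

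**What the plan says.** **Protocol 5.1, Visit 2.** The steps for all subjects include "Review and collect subject diary. Record subject-reported CTRs in the eCRF". The only Visit 2 dispensing step, "Dispense subject diary and discuss completion instructions", stands under the sub-heading "For subjects receiving a touch-up injection at Week 2". At Visit 3 (Week 6) a diary is again reviewed and collected from all subjects.

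**Protocol 3.2.2.1.** The general rule is "Diaries will be reviewed by study staff at the Week 2 visit and re-dispensed for final collection at the Week 6 visit". Touch-up subjects are the exception: "the initial diary will be collected with only two (2) weeks of diary entries completed and a second diary will be dispensed", to be collected at Week 6.

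**Protocol 5.1.1.** Visits and assessments must be carried out as set down in Section 5.1 and in the Appendix 11.1 table.

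**SAP 7.4.1.** "Each subject is expected to have diary entries from Day 1 (day of the initial injection) up to and including Day 42", or to the day of completion or discontinuation if that comes first. For a required day with no entry, "it will be assumed that on the missing days they had all those CTRs (if any") recorded for the day before or the day after, at the same severity. No maximum gap is given. Nothing says whether a filled day may itself be used to fill the next.

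**SAP 7.2.** CTR durations are tabulated by treatment in five classes: 1-3, 4-7, 8-14, 15-30 and more than 30 days.

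**The concern.** The frequency, severity and duration of diary-reported CTRs form one of the safety endpoints (Protocol 2.2.4, SAP 6.2). Protocol 7.1.8 makes CTRs subject self-reports on the diary card, so a day without a diary yields no CTR data.

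A coordinator who works through 5.1 as a checklist takes the diary back at Week 2 and gives nothing to a subject without a touch-up. Three things would follow:

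- CTRs that begin after Visit 2 would not reach the CTR tables for those subjects.
- Subjects with and without a touch-up would be observed for different lengths of time.
- The SAP would treat every day to Day 42 as a required day with a missing entry. It would then apply a fill rule that two competent programmers could implement differently.

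Daily entries that were never made cannot be recovered afterwards.

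**Working it through.** The plan gives no figure of its own on this point, so the check compares the instructions and then counts days.

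**Step 1. Diary handling after Week 2 for a subject without a touch-up**

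| Source | Diary after Visit 2? |
|---|---|
| Protocol 5.1, Visit 2 | No: collected, with no dispensing step |
| Protocol 3.2.2.1 | Yes: handed back until Week 6 |
| Protocol 5.1, Visit 3 | Implied: there is a diary to collect |
| SAP 7.4.1 | Yes: entries expected to Day 42 |
| SAP Table 1, dispensing row | Two marks and no touch-up footnote; column positions are lost in the text, so this is supporting evidence only |

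The Visit 2 list in 5.1 is the outlier.

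**Step 2. Length of the gap if 5.1 is followed literally.** Inputs: the Visit 2 window is Day 14 plus up to 3 days (Protocol 5.1), and diary entries are required to Day 42 (SAP 7.4.1).

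- Last entry Day 14: 42 − 14 = 28 missing days; 28/42 = 67%.
- Last entry Day 17: 42 − 17 = 25 missing days; 25/42 = 60%.
- If 3.2.2.1 is followed instead, the systematic gap is 0 days.

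**Step 3. What the fill rule does to a CTR still present at the last entry.** Duration = last day − onset day + 1. Counting both end days is my assumption. Filling once means only the first missing day copies a recorded day. Chaining means each filled day seeds the next, up to Day 42.

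| Onset to last entry | No fill | Filled once | Chained |
|---|---|---|---|
| Days 1-14 | 14 (8-14) | 15 (15-30) | 42 (>30) |
| Days 8-14 | 7 (4-7) | 8 (8-14) | 35 (>30) |
| Days 12-14 | 3 (1-3) | 4 (4-7) | 31 (>30) |
| Days 1-17 | 17 (15-30) | 18 (15-30) | 42 (>30) |

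The SAP class is in brackets. If only one end day counts, each figure falls by one. The first row becomes 13, 14 and 41: the single fill then stays in class 8-14, while chaining still lands above 30.

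A CTR that ended before the last diary day gains no filled days.

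**Step 4. Number of subjects.** The documents give no touch-up share. If it lay anywhere from 20% to 80%, and every site followed 5.1 literally, 52 × 0.8 ≈ 42 down to 52 × 0.2 ≈ 10 subjects would be affected. This is a ceiling under two assumptions and not an estimate.

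**The case against.** A reader of 5.1 alone might infer that all subjects without a touch-up will have no CTR data from Day 15 to Day 42. The documents do not support that. Section 3.2.2.1 provides for the diary to be handed back, the Week 6 collection step presumes it, and the SAP expects it. The intent is clear, and a site that follows 3.2.2.1 has no gap. Appendix 11.1, which shares authority with 5.1, is not in the text available here, so its diary row could not be checked.

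A reader might also infer a biased Test-versus-Control comparison. That does not follow. One diary covers both folds of a subject, so any lost days fall equally on Test and Control. Adverse events are also reviewed for every subject at Week 6, so late events need not vanish from safety reporting, although that review does not supply daily CTR severity or duration.

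On the fill rule, carrying symptoms into missing days is a conservative safety convention. The true duration inside an unobserved gap is unknown, so neither reading can be shown to be wrong. Cutting every duration at the last recorded day would shorten ongoing CTRs, and the SAP's fixed classes have no place for censored values.

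These points limit the size of the problem. They do not remove the contradiction, which sits in the section that 5.1.1 makes binding. Nor do they settle how the fill rule is to be programmed, a question that any run of several missed days raises even when diaries are handed back.

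**Conclusion.** The point holds as a contradiction between Protocol 5.1 and 3.2.2.1, joined to an under-specified rule in SAP 7.4.1.

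The loss is conditional: 25 to 28 of 42 diary days for a subject without a touch-up, at a site that follows 5.1 to the letter, and none at a site that follows 3.2.2.1. The distortion of durations is narrower still, because it touches only CTRs present at the last entry. For those it can be large: Days 1 to 14 is reported as 15 or 42 days depending on the programmer's reading. CTRs that start in the gap would simply be absent from the diary.

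The harm is mainly to absolute CTR incidence and duration, and to comparability between subjects with and without a touch-up. These conclusions rest on inclusive day counting and on Appendix 11.1 not already settling the matter.

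**What to change.** **Protocol 5.1.** Reconcile Visit 2 with 3.2.2.1 by moving the dispensing step out of the touch-up block, so that every subject leaves with a diary: the same one handed back, or a second one after a touch-up. Check that Appendix 11.1 agrees.

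**SAP 7.4.1.** Limit the fill to a stated short gap and say that filled days do not seed further fills. Report how many subjects have longer gaps and how many had a CTR ongoing at their last recorded day. The same edit can say whether both end days count in a duration.

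**Cost.** One protocol clarification, a memo to up to three sites, and a short SAP edit with one added summary. The study already uses diaries. The trade-off is that a bounded fill is less conservative than carrying symptoms forward without limit, which is why the ongoing CTRs should be counted and shown. The protocol change helps only subjects who have not yet had Visit 2, so it should come first.

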6 STUDY DEVICE AND TREATMENT OF SUBJECTS

6.1 Description of the study devices

6.1.1 *Test product*

The investigational device is a change to the Belotero Balance formulation to integrate 0.3% lidocaine hydrochloride for the purpose of pain reduction. Belotero[®] Balance with integral lidocaine is a sterile, bioresorbable, non-pyrogenic, viscoelastic, clear, colorless, homogeneous gel device. It is a bacterially fermented, injectable, hyaluronic-acid-based dermal filler. After extraction and purification, hyaluronic acid, manufactured from streptococcal cultures, is cross-linked with a binding agent 1,4-butanediol diglycidyl ether (BDDE) in two consecutively executed reactions and reconstituted in a physiologic buffer at pH 7 and concentration of 22.5 mg/mL.

Belotero Balance with integral lidocaine injectable implant will be supplied by the study sponsor. This product should be stored at room temperature (up to 25°C/77°F), away from heat, and should not be refrigerated. The test product has a clear, colorless (transparent) appearance. In the event that the syringe contains material that is not clear, do not use the syringe and notify the study sponsor.

6.1.2 *Control product*

Belotero[®] Balance is a sterile, bioresorbable, non-pyrogenic, viscoelastic, clear, colorless, homogeneous gel device. It is a bacterially fermented, injectable, hyaluronic-acid-based dermal filler. After extraction and purification, hyaluronic acid, manufactured from streptococcal cultures, is cross-linked with a binding agent, 1,4-butanediol diglycidyl ether (BDDE), in two consecutively executed reactions and reconstituted in a physiologic buffer at pH 7 and concentration of 22.5 mg/mL. Belotero[®] Balance is indicated for injection into the mid-to-deep dermis for correction of moderate-to-severe facial wrinkles and folds, such as nasolabial folds. The Belotero Balance Premarket Approval (PMA) submission (P090016) was approved November 14, 2011 by the Food and Drug Administration (FDA). Belotero filler had been previously approved for aesthetic use in the United Kingdom, Germany, Italy, Russia, Austria, and Switzerland. Currently, the approved Belotero Balance formulation does not contain lidocaine hydrochloride. The Belotero Balance package insert is included in [Appendix 11.2](#).

Belotero Balance injectable implant will be supplied by the study sponsor. This product should be stored at room temperature (up to 25°C/77°F), away from heat, and should not be refrigerated. Belotero Balance has a clear, colorless (transparent) appearance. In the event that the syringe contains material that is not clear, do not use the syringe and notify the study sponsor.

6.2 Usage

Test and control products should be used in the NLF treatment region according to the information and injection instructions presented in [Section 6.3](#). Test and control products are packaged and designed for single use only. Syringes are not to be re-sterilized. Products should not be used if the package is opened or damaged or beyond the expiration date provided to the investigational site. Please refer to the study-site binder for the expiry date memorandum from Anteis SA (manufacturer); this memo indicates the clinical trial material (CTM) lot number, the expiration date of the lot, and a statement indicating the product meets its release specifications. Do not use CTM lots beyond the expiration date indicated by the manufacturer.

6.3 Study treatment

All protocol-specific criteria for the administration of study treatment must be met and documented prior to administration of any study treatment. All device administration (injection) will be performed on site by the principal investigator (PI); only the PI can inject. The PI is also described as the treating investigator in this document. Subjects will not be dispensed any investigational material. Any noncompliant subject or site may be discontinued from the study ([Section 5.2](#)).

6.3.1 *Planned treatment procedure and administration*

Subjects will receive treatment with Belotero Balance with integral lidocaine (Test product) and Belotero Balance without lidocaine (Control product).

At baseline, approximately 52 subjects will be randomized in this split-face study. Prior to injection, one NLF will be randomized to receive Belotero Balance with integral lidocaine (Test), and the contralateral NLF will receive Belotero Balance without lidocaine (Control).

A single randomization scheme will determine which NLF (subject's right or left) will be assigned to Test product or Control product and which NLF (subject's right or left) will be injected first. Randomization will be provided by an electronic randomization system, which site personnel must access following confirmation that the subject meets all eligibility criteria.

Care must be taken to follow the subject's randomization assignment – ensuring the Test product and Control product syringes are injected according to their assigned order (Test first or Control first) and into the NLF that is randomly assigned to be injected first (subject's right NLF first or subject's left NLF first). Accurate documentation of (1) which product (Test or Control) is injected into which NLF (subject's right or left) and (2) in the order assigned by the randomization system

(subject's right NLF first or subject's left NLF first) is of critical importance in this study.

During the screening/enrollment visit, randomized subjects will receive Belotero Balance (Test and Control) in both NLFs per the administration instructions below. Each NLF of each subject will be treated until, in the agreement of the treating investigator and the subject, an optimal result is achieved, defined as “optimal cosmetic result” for the implant in that subject; however, treatment is **not to exceed the maximum allowable injection volume of 3 mL per NLF over two treatment sessions (Day 1 and optional touch-up at Week 2)**. The same injection technique (i.e., serial puncture and/or linear threading) must be used for both NLFs on Day 1. Subjects will be eligible for a single, optional touch-up treatment, at the investigator’s discretion and to achieve optimal correction, at the Week 2 visit.

Color-coded subject labels, packaged in the kit tray with the syringe and needles, will be used to document which NLF was injected with which blinded product. After receiving the randomization assignment and preparing the products for injection, these labels should be affixed to the subject’s source documents. The site personnel shall write the following on each label:

1. (R)ight or (L)eft (corresponding to the subject's right or left NLF) and
2. #1 or #2 (corresponding to which NLF was treated first or second).

This information will remain in the subject’s source documents and made available for verification of the proper randomization sequence by the sponsor or designee during monitoring visits.

Injection volumes, depth, and technique will be recorded for each NLF injection location. Observed AEs will also be recorded.

The NLF region and treatment area are shown in [Figure 5](#) and [Figure 6](#), respectively.

Figure 5: Nasolabial fold region

Crease formed lateral to the mouth from the alar-tragus to the oral commissure

[figure not shown]

Figure 7: Alar-tragus line

[figure not shown]
[figure not shown]

Figure 6: Treatment area

Injection in the nasolabial fold from the alar-tragus line to the oral commissure

6.3.1.1 *Injection procedure*

Injection occurs for all subjects at Visit 1 (baseline).

1. Prepare the pre-filled syringes of Belotero Balance (Test and Control) and the injection needle(s) before the percutaneous injection as described below. To assure proper needle attachment, use only needles provided with the clinical trial product.
2. To attach needle to syringe, open the needle packaging to expose the needle hub. Remove the Luer-syringe cap from the distal end of the syringe prior to attaching the needle.
3. Holding the Luer-lock fitting of the syringe, twist the needle onto the glass syringe provided in the kit, taking care not to contaminate the needle. Discard needle packaging. **The needle must be tightened securely to the syringe and primed with Belotero Balance (Test and Control) injectable implant. Do not over-tighten as this may break the needle and/or dislodge the syringe.**
4. Pull off the needle guard to expose needle. If excess implant is on the surface of the Luer-lock fittings, it will need to be wiped clean with sterile gauze. Slowly push the syringe plunger until the implant material exudes from the end of the needle.
5. If leakage is noted at the Luer fitting, it may be necessary to remove the needle, and clean the surfaces of the Luer fitting or, in extreme cases, replace both the pre-filled syringe and the needle.
6. Prepare subject for percutaneous injection using standard aseptic methods (e.g., alcohol, Betadine, chlorhexidine).

NOTE: In this trial, no anesthesia or other methods to minimize pain (e.g., Tylenol®, ice or ice compress, topical anesthetic, local nerve block) are allowed in either NLF before device injection through the end of the 60-minute pain assessment on Day 1 (see [Section 3.2.1.1](#)).

7. According to the subject's randomization assignment (i.e., Test or Control product injected first and subject's right or left NLF injected first), Belotero Balance (Test and Control) is to be injected into the mid to deep dermis using a 30 gauge x ½ inch needle. The injection technique (i.e., angle and orientation of the bevel, depth of injection, and quantity administered) may vary. A linear-threading technique, tunneling technique, serial puncture injections, or a combination of these have been used to achieve optimal results. Care must be used to avoid intravascular injection, with particular attention given to the region superior to the alar-tragus line (see [Figure 7](#)), regardless of technique used.

NOTE: In this trial, the maximum allowable injection volume of Belotero Balance (Test or Control) is not to exceed 3 mL per NLF over the two treatment sessions. In addition, the same injection technique (i.e., serial puncture or linear threading) must be used for both NLFs at Day 1.

8. The number of NLF injection locations and volume (not to exceed 3 mL per NLF over the two treatment sessions) of dermal filler injected are at the discretion of the treating investigator until, in the agreement of the treating investigator and the subject, an optimal result is achieved, defined as “optimal cosmetic result” for the implant in that subject. Augment to optimal 1:1 correction. Do not overcorrect.
9. For the linear-threading technique and/or tunneling technique, the needle is inserted at an approximate angle of 30° parallel to the length of the NLF. The injection can be performed with a constant low-to-moderate pressure on the plunger while slowly and gradually withdrawing the needle.
10. For the serial puncture technique, the needle is inserted at multiple sites along the NLF as per the provider’s clinical discretion.
11. With both injection techniques, slight elevation of the skin should be observed without significant blanching of the skin. To avoid visible lumps and/or discoloration, avoid injection of Belotero Balance (Test and Control) into the superficial dermis when removing the needle.
12. If immediate blanching occurs, the injection should be stopped and the area massaged until it returns to a normal color. Blanching may represent a vessel occlusion. If normal skin coloring does not return, do not continue with the injection. Treat in accordance with the American Society for Dermatologic Surgery guideline, which includes **possible** hyaluronidase injection.
13. When the injection is complete, the site may be gently massaged, if necessary.

NOTE: In this trial, after completion of the 60-minute VAS pain assessment (see [Section 3.2.1.1](#)), ice, cold compresses, and/or other medication(s) to minimize swelling and bruising are permitted at the discretion of the treating investigator.

14. Immediately stop the injection if a study subject exhibits any of the following symptoms: changes in vision; signs of a stroke; blanching of the skin; or unusual pain during or shortly after the procedure. Subjects should receive prompt medical attention and possibly evaluation by an appropriate healthcare practitioner specialist should an intravascular injection occur.

Subjects must be also be informed that, at any time over the study interval, if they experience signs or symptoms of an intravascular injection, similar to those noted above, or symptoms listed on the first page of the study diary

card or within the informed consent form, they must seek immediate medical attention and notify the study doctor immediately. The study doctor must refer the subject to a specialist if additional medical attention is deemed necessary.

6.3.1.2 *Maximum injection volume*

In this study, the maximum injection volume of Belotero Balance (Test or Control) is not to exceed 3 mL per NLF over the two treatment sessions (Day 1 and optional touch-up injection at Week 2). Subjects should not receive more than 6 mL of Belotero Balance per year. The safety of injecting greater amounts has not been established.

6.4 *Packaging of treatment supplies*

Belotero Balance with integral lidocaine (Test product) and Belotero Balance without integral lidocaine (Control product) will be provided by the study sponsor. The sponsor will package study materials according to applicable regulatory requirements. The sponsor will provide all pertinent labeling information, as well as a description of the specific device-packaging conditions.

The sponsor will provide a blinded, bulk supply of both Test product and Control product. The product kits, including syringe and needles, will be distinguished only by different colored labels. Only the unblinded sponsor will have the product lot number key (i.e., code break).

Product kits will include:

- One sterile 1-mL prefilled glass syringe of Belotero Balance with integral lidocaine (Test) or
- One sterile 1-mL prefilled glass syringe of Belotero Balance without integral lidocaine (Control);
- Two sterile 30 gauge, ½ inch needle(s) with Luer-lock fittings; and
- Color-coded subject labels (provided in the kit tray) for appropriate source documentation.

6.5 *Receipt, storage, dispensing, and return/disposal*

Upon receipt, the site personnel will verify the contents of all study supplies received and promptly notify the appropriate contacts of any discrepancies or damages. The investigator is responsible for ensuring that an accurate record of inventory is maintained. The investigator will keep a current record of the study product delivery to the study site,

inventory, and dispensing, and this record will be made available to the sponsor upon request. Study sites will be queried about any discrepancies.

All study devices must be stored in a secure, environmentally controlled, monitored area in accordance with the labelled storage conditions.

Only authorized study personnel may supply, dispense, and/or administer study treatment, and only subjects enrolled in the study may receive study treatment. The investigator is responsible for maintaining a current, accurate record of all study treatment dispensation.

Any used syringes of Belotero Balance (Test and Control) and needles should be discarded per the appropriate handling and disposal procedures at the site. Any unused/unopened product, needles, and/or outer packaging (of used kits) should be retained so the monitor can perform device-accountability procedures.

At the end of the study and after verification of study device/kit accountability, it is the investigator's responsibility to return or destroy all unused study supplies, as directed by the sponsor. Appropriate records of return or disposal must be maintained for accountability purposes. For the return of supplies, the following address shall be used:

To: Merz North America, Inc.
Attn: Receiving
[name]
[name]

[contact]
[contact]

All study-accountability procedures must be completed before the study is considered complete.

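### Kit labels that differ only by colour could let the blinded injector learn the code across subjects; kit numbers issued by the randomization system would be a cheap improvement

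*Protocol*

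**What the plan says.** **Supply and labels.** Protocol 6.4: "The sponsor will provide a blinded, bulk supply of both Test product and Control product", and "The product kits, including syringe and needles, will be distinguished only by different colored labels". The code break is a key of product lot numbers held by the unblinded sponsor. The same section adds: "The sponsor will provide all pertinent labeling information, as well as a description of the specific device-packaging conditions". That material is not among the documents reviewed.

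**Use of the labels at the site.** Under Protocol 6.3.1 the color-coded labels "will be used to document which NLF was injected with which blinded product". "The site personnel shall write the following on each label": the side (R or L) and the order (1 or 2). The labels stay in the source documents, "made available for verification of the proper randomization sequence by the sponsor or designee during monitoring visits".

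**Randomization.** Protocol 3.1, 5.1, 6.3.1 and 8.2 between them describe the assignment of product to fold and of injection order, through an electronic system. None of them mentions a kit number.

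**Other identifiers.** Protocol 6.2 places a manufacturer's memo with lot number and expiry date in the site binder. Protocol 6.6 asks the accountability log to identify each device by batch or serial number or by a unique code, without choosing among them.

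**People.** Protocol 3.1 and 6.7 blind the treating investigator. Protocol 6.3 says "only the PI can inject". Under 3.2.1.1 the investigator or the coordinator asks each subject which side was less painful and records the answer in the source documents and the eCRF. Investigators sign the eCRFs (9.5.2). The SAP says nothing on packaging.

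**The concern.** One person at each site treats every fold, sees every label, and may learn which side hurt less. If a colour stands for the same product in successive subjects, each answer is a clue to the code, and the clues add up.

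What is open to influence is what the plan leaves to that person. Protocol 6.3.1.1 (steps 7 and 8) leaves needle angle, depth, quantity and number of injection locations to the injector. It does so within limits: the same technique in both folds on Day 1, mid to deep dermis, a 30-gauge needle, 1:1 correction without overcorrection, and the subject's agreement that the result is optimal. The same investigator decides on touch-up at Week 2 (5.1) and on whether a diary-reported treatment response becomes an adverse event (8.4.2.1). Adverse events are then tabulated by Test and Control.

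An emergency code break (7.4) has a related weakness. If the broken fold's colour or lot is shared, the answer carries over to other subjects.

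**Working it through.** **1. Would colour identify product?** Set 6.4 beside 6.3.1. Kits come in bulk and differ only by label colour, so two kits of one colour cannot be told apart at the site. Staff can give the assigned product only if all kits of that colour, within that supply, hold the same product. The described handwriting adds side and order, so colour is the only product information described on the label. Two things stay open: how many colours each product has, and whether colours differ between sites. The log entry in 6.6 does not settle this, because a batch number could also follow product and the entry is not tied to randomization.

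**2. The plan's own figure.** Inputs from Protocol 8.1: difference 3.8 cm, SD of difference 7, one-sided α 0.025, power 95%. A paired t-test with the noncentral t gives power 0.9497 at n = 46 and 0.954 at n = 47. The stated 47 reproduces. Nothing below changes it.

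**3. One subject.** With normal differences, P(Test rated less painful) = Φ(3.8/7) = Φ(0.543) = 0.706.

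**4. Majority guess after five subjects, all answers known, no ties.** With p = 0.706: 10p³(1−p)² + 5p⁴(1−p) + p⁵ = 0.304 + 0.366 + 0.176 = 0.845 (unrounded terms).

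**5. Less favourable assumptions for the guesser** (the shares are assumed, not in the documents):

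| Answers known | Share answering no difference | Right | Undecided | Wrong |
|---|---|---|---|---|
| All | 0 | 0.845 | 0 | 0.155 |
| All | 10% | 0.779 | 0.088 | 0.133 |
| All | 30% | 0.711 | 0.150 | 0.138 |
| Half | 0 | 0.644 | 0.201 | 0.155 |
| Half | 30% | 0.569 | 0.268 | 0.163 |

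**6. How much a new label scheme removes.** Before a new subject's injection, codes that do not repeat by product leave the guess at 0.50. By Week 2 the investigator may already know this subject's own Day 1 answer, which points to the Test fold with probability 0.706 whatever the label says. Adding five earlier subjects under a fixed colour gives six answers. P(4 or more right) = 15p⁴(1−p)² + 6p⁵(1−p) + p⁶ = 0.756, and P(3 of 6) = 20p³(1−p)³ = 0.178. With ties split, 0.756 + 0.178/2 = 0.845. The gain at that stage is from about 85% to about 71%.

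**7. How rough the model is.** A difference on a 10-cm scale must lie between −10 and +10. The normal model puts 1 − Φ((10 − 3.8)/7) = 18.8% above and Φ((−10 − 3.8)/7) = 2.4% below, about 21% in all. The plan calls SD 7 conservative. With an assumed SD of 5, step 4 gives 0.922.

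**8. Code break.** 52/3 = 17.3 subjects per site if enrolment is even, so about 16 others.

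**9. Kits.** With 1-mL single-use syringes and 3 mL per fold, 52 × 2 × 3 = 312. If splitting the volume over two sessions takes a fourth syringe, 52 × 2 × 4 = 416.

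**The case against.** The strongest reply is that the documents never say one colour means one product for every subject. The labelling information promised in 6.4 is not before us, and 6.6 allows a unique code. This stands as a limit on certainty. It does not remove the point: 6.4 as written makes colour the only distinction, and a unique code in an accountability log is not a kit assignment made by the randomization system.

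A reader might infer that the blind is broken or that the primary result is biased. The documents do not support that. Subjects rate their own pain, and side and order are randomized. The Week 6 evaluator is kept away from procedures and records (3.2.1.2.1). If lidocaine had no effect, pain answers could not reveal the colour, so learning from pain is not mainly a false-positive risk. Nor does the investigator necessarily hear every answer or handle every kit: the coordinator may ask the questions, and other authorized staff may dispense (6.5).

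A reader might also infer that kit numbers would return every later judgement to chance. They would not. The subject's own Day 1 answer, the reaction to the first fold, and numbness recorded in the diary all remain as cues within the subject.

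The count of 16 is a maximum. It includes subjects already treated and rated, whose Day 1 injection and VAS can no longer be affected.

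Finally, numbered kits bring a mix-up risk, and 6.3.1 stresses accurate recording of which product went into which fold. That is a real cost and is counted under the fix.

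**Conclusion.** The point holds as a cheap improvement to blinding logistics, not as a demonstrated unblinding. On the text of 6.4, colour would track product within a supply, and the only injector at a site could connect colour with pain answers from one subject to the next.

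The main exposure is the injector's discretion over volume and number of injection locations on Day 1 in later subjects. Touch-up decisions and the step from treatment response to adverse event are exposed less, because within-subject cues exist there anyway. No size of bias in the VAS can be derived from the documents, and none is claimed.

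The figures (71% for one subject; about 85% after five if every answer is known and none is a tie; 57% to 78% under the weaker assumptions) illustrate guessability only. They rest on a colour that is constant by product, independent normal differences, and the plan's 3.8 cm and SD 7, a model that puts about a fifth of differences outside the possible range. The code-break figure of about 16 also assumes even enrolment at three sites. Confidence is medium, because the labelling details are not visible.

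**What to change.** **Protocol 6.4.** Label kits with unique numbers, or with codes that do not repeat by product, and have the electronic randomization system assign them to each fold, including touch-up and replacement kits. Use the unique-code option in 6.6. Keep any colour or lot identifier that the site can see from being constant by product, and align the lot memo in 6.2 with this. If colours already vary so that they do not identify product across subjects, one sentence in 6.4 saying so is enough.

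**Cost.** Relabelling before shipment and a kit list of at least 312 to 416 numbers, plus buffer stock and replacements for the faulty syringes foreseen in 6.3.1.1 (step 5). The randomization system may need a kit module, since the documents do not say that it manages kits. Volume is settled during the injection, so further 1-mL kits may have to be matched to a fold mid-procedure; the site instructions need a check against mix-ups. Sample size, visits and analyses do not change.

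**Limit.** The change removes learning across subjects and confines an emergency code break to the subject concerned. It does nothing about cues within a subject.
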